5.1 PROCEDURES

A detailed schedule of assessments by visit is shown in Table 5 below.

Table 5: Schedule of events

| Study Period | Screening | Enrollment | Treatment Period | | | Follow Up |
|-----------------------------------|-----------|------------|------------------|----------------|------------------|------------------|
| | | | Visit | V3 | V4 | |
| Visit | V1 | V2 | V3 | V4 | EOT ⁶ | SFU ⁷ |
| Total duration (weeks) | - 4 weeks | 0 | 2 | 4 | 6 | 12 |
| Visit windows (weeks) | | | ± 2 days | ± 2 days | ± 2 days | ± 5 days |
| Written informed consent | X | | | | | |
| Eligibility criteria | X | X | | | | |
| Medical history ¹ | X | X | | | | |
| Physical examination | X | | X | X ² | X | X |
| Complete Neurological examination | X | X | X | X | X | X |
| Anthropometrics | X | X | X | X | X | X |
| Vital signs ³ | X | X | X | X | X | X |
| Laboratory testing | X | | X | X | X | X |
| Serum Pregnancy test ⁴ | X | | | X | | X |
| Urine pregnancy test | | X | | | | |
| Study medication dispense | | X | X | X | | |

| | | | | | | |
|-------------------------------|----------------|---|---|---|---|---|
| Medication compliance audit | | | X | X | X | |
| Concomitant medication review | X | X | X | X | X | X |
| Seizure Frequency review | X | X | X | X | X | X |
| Adverse Events | | | X | X | X | X |
| ECG | X ⁵ | | X | | | X |

1. Medical history and Epilepsy history, including other relevant baseline disease characteristics. All available epilepsy history will be collected. Other Medical history will be collected for the past 12 months.
2. Abbreviated physical exam
3. Blood pressure, heart rate, breathing rate, and temperature.
4. Only for female patients of childbearing potential.
5. For screening, the results of a clinically indicated ECG, found to be non-clinically significant within the last 4 weeks can be utilized.
6. EOT may occur prior to 6 weeks if participant is discontinued or withdrawn before completing entire study as per protocol. In the case of withdrawal, the EOT visit should be completed within 2 weeks of the date of withdrawal.
7. SFU visit may occur prior to 12 weeks if participant is discontinued or withdrawn before completing entire study as per protocol. In the case of withdrawal, an SFU visit (or at minimum telephone contact) should be completed within 6 weeks of the EOT visit.

5.1.1 SCREENING EXAMINATION AND ELIGIBILITY SCREENING FORM – VISIT 1

All participants must sign and date the most current Institutional Review Board (IRB)-approved written informed consent before any study-specific assessments or procedures are performed. A screening number will be allocated to each participant. An Eligibility Screening Form (ESF) documenting the investigator’s assessment of each screened participant with regard to the protocol’s inclusion and exclusion criteria will be completed by the investigator. A screen failure log will be maintained by the investigator.

The following study-specific activities will be completed at the screening examination:

- Medical history: Medical history for the past 12 months and all Epilepsy history will be abstracted from participant’s hospital medical record and patient interview.
- Physical examination: the investigator will conduct a complete physical and neurological examination
- Anthropometrics: height and weight will be taken
- Vital signs: blood pressure and heart rate, breathing rate, and temperature will be taken

- Baseline laboratory testing (see [Section 5.3.2.4](#) for description of laboratory testing): This will be done through a service contract via Calgary Lab Services. The Calgary Lab Services reference range will be utilized to assess the clinical relevance of results.
- Pregnancy test: a serum pregnancy test will be administered to all sexually active females of post-menarche status. All heterosexually active males and females will be counseled on the use of appropriate contraceptives during study participation.
- Concomitant medications: will be collected to ensure that the patient is not on any prohibited medications
- Seizure frequency: current seizure types and frequency will be reviewed. Proper seizure tracking will be reviewed with the participant/patient and family; participants will be encouraged to download and use the Seizure Tracker app on their smart phone. Participants will be asked to track their seizures for the duration of the screening period.
- ECG: An ECG will be collected through a service contract via the Cardiology department at the ACH. Participants who have had a clinically indicated ECG, found to be non-clinically significant, within 1 month prior to screening will not require another ECG, provided the investigator deems the participant stable. The ECG may be collected at any point following the screening visit until enrollment visit (Visit 2), as long as results are available and may be reviewed by the investigator prior to enrollment

5.1.2 ENROLLMENT VISIT – VISIT 2

Participants meeting all inclusion and no exclusion criteria will be enrolled. Participants will receive study medication at this visit.

The following study specific activities will be completed at the enrolment visit (Visit 2):

- Medical history: Medical history and Epilepsy history will be reviewed once again to ensure that any new history since screening is captured.
- Anthropometrics: height and weight will be captured to establish baseline growth and to calculate body surface area (BSA) for proper medication dosing
- Vital signs: blood pressure and heart rate
- Pregnancy test: a urine pregnancy test will be done for all applicable participants
- Study medication dispensed: Study medication will be prepared and dispensed by the ACH research pharmacy, with dosage based on participant BSA ([see Section 6.1](#)). Participants will be counseled by the investigator on: how to take the medication, including to consume enough fluids to maintain adequate daily hydration, as adjusted for age; to contact the investigator promptly if excessive vomiting/diarrhea; or dizziness, palpitations, syncope, or increased seizures develop; or to contact the investigator immediately or present to the emergency room if leg swelling, chest pain, or shortness of breath develop. Participants will take VOR, 230 mg/m² once daily, preferably at the same time of the day throughout the treatment portion of the study, in addition to their prescribed evidence-based medical care for seizure management.
- Participants will be given enough study medication to last until the next study visit plus 2 days in the event that the participant cannot make this visit. In this case, the study coordinator will ensure, via phone communication, that participant is not missing a visit due to AEs. In the event of an AE, the investigator will speak to participants/caregivers to give further instruction. If patient is hospitalized, appropriate SAE measures will be undertaken. If participants need to reschedule beyond the 2-day window, additional study

medication may be prescribed by the investigator and dispensed by the ACH research pharmacy on a case by case basis. Participants will not be given medication if the following visit is also missed, without explicit permission by the investigator.

- Concomitant medications: will be reviewed again to ensure that information has not changed since screening visit
- Seizure frequency: current seizure types and frequency will be reviewed. Proper seizure tracking will be reviewed again with the participant/patient and family.

5.1.3 ASSESSMENTS AND PROCEDURES DURING THE TREATMENT PERIOD

Participants will be required to undergo regular visits during the treatment period for the assessments of safety/tolerability and efficacy as outlined in [Table 5: Schedule of events](#)

. They will visit the study center at 2-, and 4 weeks, at 6 weeks for the EOT visit, and 6-weeks after the EOT for the SFU visit. If a participant is discontinued from study medication and/or withdrawn prior to completing the study as per protocol, the EOT visit may occur prior to 6 weeks following enrollment. The SFU visit should be completed within 6 weeks of medication discontinuation.

In addition, the following evaluations will be performed at each visit at the clinic throughout the treatment period:

- Physical examination: standardized physical examinations will be performed at all study visits; an abbreviated physical exam will be conducted at Visit 4 (week 4 visit)
- Complete neurological examination: a complete neurological examination will be completed at all study visits.
- Anthropometrics: height and weight will be captured at all study visits to assess for appropriate growth and for proper medication dosing
- Vital signs: will be captured at all study visits
- Laboratory monitoring: participants will visit the lab for testing at all study visits during this period. Investigators will contact participants if results warrant intervention prior to the next scheduled visit.
- Pregnancy test: Serum pregnancy test will be taken at Visit 4.
- Study medication dispensing and medication compliance: Following investigator recommendation, participants will receive new drug supply at each defined visit. Participants will be required to bring in old unused drug for assessment of compliance. The importance of compliance will be emphasized at each visit. Participants will also be reminded to strive to consume enough fluids to maintain adequate daily hydration, as adjusted for age. Medication will not be dispensed at the EOT visit.
- Concomitant medications: will be reviewed at each study visit.
- Review of AE: Participant's AEs will be reviewed at each study visit. However participants are encouraged to inform investigators about occurrence of AEs as soon as possible; i.e. not wait until their next scheduled visit.
- Seizure Frequency: Participants will be asked to provide their seizure tracker information since the last study visit. Participants' seizure types and how to accurately record seizure frequency will be reviewed by the investigator at each study visit. If participants commence to exhibit new seizure types, they will be asked to collect the seizure frequency of the new seizure type.
- ECG: an ECG will be conducted on Visit 3. The ECG may be collected within 1 week prior to study visit depending on appointment availability at the ECG lab.

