3.1.2 PHASES OF STUDY

There are three phases to the study.

Phase 1: Screening period

During this phase, participants will be screened for study eligibility, which will last a total of 4 weeks. This will include several baseline investigations including full review of medical history and current medications, seizure frequency, physical examination, vital signs, laboratory safety testing, pregnancy testing for eligible patients, and electrocardiogram (ECG) (see Section 5 Schedule of Assessments and Procedures for complete list of screening procedures). In addition, baseline seizure frequency will be determined during this period. Clinically stable participants, fulfilling all eligibility criteria (see sections 4.2 and 4.3) will be enrolled in the treatment period of the study.

Phase 2: Treatment period

The duration of the treatment period will be 6 weeks. VOR will be given as fixed doses of 230 mg/m²/day. Following the enrollment visit, participants will visit the clinic for 2 more visits every 2 weeks, plus an end of treatment (EOT) visit (see Section 5.1 for detailed schedule). Participants may be seen more frequently for unscheduled visits for follow up of AEs, etc. as per the investigator's discretion. Study visits will include a physical examination, height and weight measurement, vital signs, pregnancy testing (required patients only). Safety monitoring during the treatment period will include laboratory safety testing and ECG. Investigators will review current medications, AEs, seizure diary/frequency at each visit. Investigators will assess study medication adherence at all visits; unused study medication will be returned to site at each visit and new study medication will be dispensed by local pharmacy, as recommended by the investigator. Unused study medication will be destroyed as per local standard operating procedures. All assessments and visit procedures will occur as stipulated in Section 5: Schedule of Assessments and Procedures.

Phase 3: Follow-up period

A safety follow-visit (SFU) will take place 6 weeks after the EOT Visit. The SFU visit will include a physical examination, height and weight measurement, vital signs. Safety monitoring for this visit will include laboratory safety testing and ECG. Investigators will review AEs since last visit and seizure diary/frequency. Any ongoing AEs will be followed by the investigator until resolution or stability.

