5.1.4 SAFETY FOLLOWUP

An SFU for all participants, including patients prematurely withdrawn from treatment, will be conducted 6 weeks after the EOT visit. This visit will include:

- Physical examination
- Complete neurological examination
- Anthropometrics
- Vital signs
- Laboratory monitoring. Participants will be contacted with results requiring intervention
- Pregnancy test: a serum pregnancy test will be taken for applicable participants.
- Concomitant medications
- Seizure Frequency
- Review of Adverse Events
- Review of seizure frequency
- ECG: may be collected within 1 week prior to study visit.

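### For participants who stop drug early, the SFU timing rules contradict each other when EOT is late, and two of them set no earliest date

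*Combined protocol and SAP*

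**What the plan says.** Four places in the combined protocol and SAP set the SFU date.

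- Section 3.1.2 (Phase 3): "A safety follow-visit (SFU) will take place 6 weeks after the EOT Visit". The visit list in 5.1.3 agrees: "6-weeks after the EOT for the SFU visit".
- Section 5.1.4 applies the same timing and names early withdrawals: "An SFU for all participants, including patients prematurely withdrawn from treatment, will be conducted 6 weeks after the EOT visit".
- Section 5.1.3, directly after its sentence on early discontinuation: "The SFU visit should be completed within 6 weeks of medication discontinuation".
- Table 5 footnote 7, for withdrawals: "an SFU visit (or at minimum telephone contact) should be completed within 6 weeks of the EOT visit".

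Footnote 6 controls how late EOT can be: "the EOT visit should be completed within 2 weeks of the date of withdrawal". Table 5 gives the SFU a window of ±5 days.

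The other follow-up periods run from the last dose. Section 7.2.1 collects AEs for up to 6 weeks after it, and 7.2.2 monitors SAEs over the same period. Section 4.7 places the chart review for those lost to follow-up 6 weeks after the last assumed dose. Section 8.2.2.1 analyses AEs at 42 days after discontinuation, and ends the analysis period at SFU completion or at 42 days after the last dose. Section 4.7 mentions a telephone SFU only for those who withdraw consent to further follow-up.

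**The concern.** The rules differ in anchor (EOT or last dose) and in kind (a fixed time or only a latest date). For completers this hardly matters: "Medication will not be dispensed at the EOT visit", so their last dose is presumably close to EOT. For early stoppers EOT can trail the last dose by up to two weeks, and the anchors separate.

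Two things follow. First, a site can face instructions that cannot both be obeyed. Second, the two rules worded as a latest date are satisfied by an SFU held soon after EOT, and footnote 7 is satisfied by a call that yields no laboratory test, ECG or examination.

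Related AEs are part of the primary endpoint (8.1.1), and many early stoppers will have stopped for toxicity. Haematologic effects and QTc prolongation are named safety concerns (7.1.3.1), and both need a blood test or a tracing to detect. Table 5 schedules ECGs at screening, Visit 3 and SFU only. For a child who stops before Visit 3, the SFU ECG is therefore the only one scheduled after screening.

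**Working it through.** **Inputs.** Let d be the number of days from last dose to EOT, with 0 ≤ d ≤ 14 (footnote 6). This takes withdrawal date as last-dose date; if drug stops before formal withdrawal, d can be larger. Six weeks is 42 days. The SFU window is ±5 days (Table 5). The plan states no figure of its own to reproduce.

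**Rules, in days after last dose.**
- 3.1.2 and 5.1.4: d + 42, or d + 37 to d + 47 with the window.
- 5.1.3: no later than 42, with no earliest day.
- Footnote 7: no later than d + 42, with no earliest day after EOT.

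| d | 5.1.4 target | 5.1.4 with ±5 | 5.1.3 latest | Both met? |
|---|---|---|---|---|
| 0 | 42 | 37–47 | 42 | yes |
| 5 | 47 | 42–52 | 42 | yes, on day 42 only |
| 6 | 48 | 43–53 | 42 | no |
| 10 | 52 | 47–57 | 42 | no |
| 14 | 56 | 51–61 | 42 | no |

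**Conflict.** Both rules hold when d + 37 ≤ 42, that is d ≤ 5; they conflict for d = 6 to 14. If the ±5 days is also added to the 5.1.3 limit (42 + 5 = 47), both hold when d + 37 ≤ 47, that is d ≤ 10, and the conflict is confined to d = 11 to 14. Footnote 7 can be met together with either rule.

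**Does the conflict lose data?** For d = 6 to 14, following 5.1.4 puts the SFU on days 43 to 61. Following 5.1.3 at its 6-week mark puts it on day 42. Both reach the 42-day time point, so the conflict alone costs no follow-up.

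**Missing lower limit.** An SFU soon after EOT, before day 42, satisfies 5.1.3 and footnote 7 together. Only 3.1.2 and 5.1.4 forbid it. This is the route by which follow-up could be shortened.

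**End of the AE window in 8.2.2.1.** With d = 14, SFU completion under 5.1.4 is day 56 (51–61). The alternative end point is day 42. The two differ by 56 − 42 = 14 days (51 − 42 = 9 to 61 − 42 = 19).

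**How many participants.** At the adult AE discontinuation rate of 10.5% (1.1.4.3): 0.105 × 12 = 1.26. At the 30% ceiling in 5.2.1: 0.30 × 12 = 3.6. The documents do not say how EOT dates would be distributed, so the number with d of 6 or more cannot be estimated.

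**The case against.** The strongest reply is that the mandatory rule for these participants already exists. Sections 3.1.2 and 5.1.4 say *will*, and 5.1.4 names prematurely withdrawn patients; 5.1.3 and footnote 7 say only *should*. The intended 6 weeks is clear. AE collection also does not hang on the visit date: 7.2.1 and 7.2.2 set their own periods, 5.3.1 collects AEs throughout the study, 7.1.3 follows known events to baseline or stability, and "participants are encouraged to inform investigators about occurrence of AEs as soon as possible". Section 4.7 asks for a full evaluation at the time of withdrawal, which points to a small d, where the rules agree. Section 4.8 removes non-safety stops within 14 days from the final analysis, so the ECG example mainly concerns safety stops, for whom extra ECGs are available at discretion (7.1.3.1). The telephone option is worded as a minimum, not as an equal alternative.

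All of this stands as a limit on size. It does not reconcile 5.1.3 with 5.1.4 for a late EOT, and it leaves a site that reads only 5.1.3 and footnote 7 with permission to hold an early or telephone SFU. Spontaneous reporting does not replace a scheduled blood count or ECG.

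A reader might infer that the conflict itself causes AEs to be missed, or that the length of follow-up is undefined. The documents support neither. Both anchors reach day 42 when used at 6 weeks, and 3.1.2, 5.1.4 and 8.2.2.1 make the intended period plain.

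**Conclusion.** The contradiction is real but conditional: it arises when EOT falls 6 to 14 days after the last dose (11 to 14 on the most lenient reading of the window). The practical exposure is the absence of an earliest date in 5.1.3 and footnote 7, together with the telephone allowance. What could be under-collected is new non-serious, laboratory and ECG findings before day 42 in a few early stoppers, about 1.3 to 3.6 of 12 if only AE stops are counted. Later non-safety stops would add to this, but no rate is given.

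It would be wrong to read this as a threat to the whole primary endpoint. SAE reporting (7.2.2) and discontinuation counts are unaffected, and the study is a small descriptive pilot. Severity is minor. The conclusion rests on taking withdrawal date as last-dose date and on applying the ±5-day window to early stoppers.

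**What to change.** For early stoppers, use one anchor and give it a lower limit:

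1. Set the SFU at 42 to 47 days after the last dose in the final SFU sentence of 5.1.3, in 5.1.4 and in footnote 7, with a matching exception in 3.1.2. A symmetric ±5 days should not be used, because it would allow day 37, before the analysis time point.
2. In footnote 7, limit a telephone SFU to those who decline clinic follow-up, in line with 4.7.
3. In 8.2.2.1, count AEs with onset through 42 days after the last dose, list later events separately, and flag anyone last contacted before day 42.

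Section 7.2.1 needs no change, and completers are unaffected by the visit rule.

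The cost is wording in five places and no new visit. The downsides are a shorter EOT-to-SFU interval when EOT is late (42 − 14 = 28 days if EOT is on day 14) and a separate listing for events after day 42.

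### No pregnancy test is scheduled at the end-of-treatment visit, so a girl who stops before Visit 4 has no post-dose test until a safety follow-up that may be a telephone call

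*Combined protocol and SAP*

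**What the plan says.** Table 5 schedules serum pregnancy tests at Visit 1, Visit 4 and the SFU, and a urine test at Visit 2. The cells for Visit 3 and EOT are blank.

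The running text agrees, so the blank EOT cell is not an artefact of table extraction:

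- Section 5.1.1 has a serum test at screening.
- Section 5.1.2, the visit at which drug is first dispensed, says "a urine pregnancy test will be done for all applicable participants".
- Section 5.1.3 says "Pregnancy test: Serum pregnancy test will be taken at Visit 4".
- Section 5.1.4 has a serum test at the SFU.
- Section 5.3.2.5 ties serum testing to Table 5, and the laboratory panel in 5.3.2.4 contains no hCG.

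Blood is nevertheless taken at EOT. Section 5.1.3 says "participants will visit the lab for testing at all study visits during this period", and Table 5 marks laboratory testing at EOT.

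For early stoppers, Table 5 note 6 says "the EOT visit should be completed within 2 weeks of the date of withdrawal" and note 7 says "an SFU visit (or at minimum telephone contact) should be completed within 6 weeks of the EOT visit". Section 5.1.3 times the SFU differently: "The SFU visit should be completed within 6 weeks of medication discontinuation". Section 5.1.4 says "An SFU for all participants, including patients prematurely withdrawn from treatment, will be conducted 6 weeks after the EOT visit". Section 4.7 plans both an EOT and an SFU visit for a participant who stops treatment only. It mentions a phone SFU where consent to further follow-up is explicitly withdrawn.

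**The concern.** The actions in 7.2.3 (counselling on possible fetal effects of early exposure, and follow-up to the end of the pregnancy) can start only when the pregnancy is known. The only scheduled test between the first dose and the SFU is at Visit 4. A participant who stops before it goes through EOT, gives blood there, and is not tested.

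If her SFU is then a telephone call, discovery depends on her reporting the pregnancy herself, as 7.2.3 instructs. Section 1.1.4 leans on valproate as a drug of the same class, and 1.1.4.2 records teratogenicity concerns about valproate. Early knowledge of an exposed pregnancy is therefore not a trivial matter here. What is at stake is patient safety; no endpoint or analysis depends on it.

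**Working it through.** The plan gives no figure to reproduce. The check is a count of scheduled tests by path, then timing, then numbers.

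**1. Scheduled pregnancy tests after the first dose.** The Visit 2 urine test is taken as preceding the first dose.

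| Path | As planned | With a test at EOT |
|---|---|---|
| Completer | 2 (Visit 4, SFU) | 3 |
| Stops before Visit 4, SFU in person | 1 (SFU) | 2 |
| Stops before Visit 4, SFU by telephone | 0 | 1, if she attends EOT |
| Stops after Visit 4, SFU by telephone | 1 (Visit 4) | 2 |

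**2. Completers.** Inputs from Table 5: Visit 4 at day 28 (26 to 30), EOT at day 42 (40 to 44), SFU at day 84 (79 to 89).

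- Visit 4 to the next scheduled test: 84 − 28 = 56 days, or 8 weeks (79 − 30 = 49 to 89 − 26 = 63).
- With a test at EOT: 42 − 28 = 14 days (40 − 30 = 10 to 44 − 26 = 18).
- Conceptions found sooner: if hCG becomes detectable L days after conception, Visit 4 finds conceptions up to day 28 − L and EOT finds them up to day 42 − L. The gain is (42 − L) − (28 − L) = 14 days of conceptions for any L (10 to 18 with windows).
- How much sooner: SFU minus EOT = 42 days, or 6 weeks (37 to 47 if the ±5-day window is applied from the EOT date).

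**3. Early stoppers.** Take a girl who stops and withdraws on day s, before day 28.

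- EOT is due by s + 14 (note 6).
- The SFU is due by s + 42 under 5.1.3, or by s + 14 + 42 = s + 56 under notes 6 and 7.
- Example with s = 14: a test at EOT would come by day 28. The SFU test, if in person, could come as late as day 56 or day 70.
- Her last scheduled test before that is the day-0 urine test.

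**4. How many participants.**

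- Section 5.2.1 expects discontinuation for intolerable adverse events of up to 30%, and 3.3 gives 12 participants: 0.30 × 12 = 3.6 at most, of either sex and any age.
- Share of dosing days before Visit 4: 28/42 = 67% (26/42 = 62% to 30/42 = 71%). This is a share of days, not a probability for any participant.
- Assuming stops are spread evenly over dosing: 3.6 × 28/42 = 2.4 before Visit 4.
- Assuming 0 to 3 of the 12 are females of childbearing potential, with the same stopping rate as the others: 2.4 × 0/12 = 0 to 2.4 × 3/12 = 0.6.

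This is before requiring a telephone SFU or a conception, both of which lower it. Withdrawals for other reasons would raise it, but the protocol gives no rate for them.

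**The case against.** The strongest reply is that the path with no test is not what the protocol intends. Section 4.7 sends a participant who only stops the drug to an EOT visit and an SFU visit, and 5.1.4 plans a serum test at the SFU for everyone, early withdrawals included. The phone SFU in 4.7 belongs to withdrawn consent, and the telephone wording in note 7 reads most naturally as a fallback. This largely stands. A reader might infer that the schedule routinely leaves early stoppers untested, and the documents do not support that. What remains is that note 7 is worded for any withdrawal, so the protocol leaves the telephone route open more widely than 4.7 does.

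A second reply is that the SFU test covers conceptions during dosing better than an EOT test would, since it comes 6 weeks after the last dose. That is right for completers, and it is why their pregnancies are found late rather than missed. It does not help where the SFU is a call.

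A third is that numbers are tiny. Sections 5.1.1 and 5.3.2.5 restrict testing to sexually active girls, and exclusion criterion 16 removes heterosexually active participants unwilling to use highly effective contraception. This also stands and limits the size.

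A reader might also see a contradiction with 3.1.2, which lists pregnancy testing among treatment-period visit procedures without naming a visit. That passage closes by deferring to Section 5, and it treats the ECG in the same loose way. It is a summary, not a rival schedule.

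**Conclusion.** The point holds as a minor safety-monitoring gap. No pregnancy test is scheduled at EOT although blood is drawn there. A female of childbearing potential who stops before Visit 4 has no scheduled post-dose test until the SFU, and she may have none if the telephone option in note 7 is used. For completers the effect is delay only: about 42 days for a 14-day span of conceptions.

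The estimate of 0 to 0.6 girls rests on the 30% discontinuation ceiling, evenly spread stops and an assumed 0 to 3 females of childbearing potential among the 12. The true number may be zero. No endpoint or analysis is affected.

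A reader might go further and infer from the 90-day pregnancy follow-up in 7.2.3 that a post-treatment contraception period has been left out. The documents do not support that: they nowhere make 90 days a contraception requirement, and the consent pages, which could state a period, are not among the text available.

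**What to change.** Two changes at the next amendment:

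1. In Table 5 and 5.1.3, add serum hCG to the blood already drawn at EOT, including an early EOT, for females of childbearing potential.
2. Reword Table 5 note 7 to match 4.7, so that telephone contact replaces the SFU visit only when consent for follow-up is withdrawn or the visit cannot be obtained.

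The cost is one assay on an existing sample for a few girls, possibly none, plus the wording. There is no extra visit or venepuncture.

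The limits should be accepted openly. For completers, dosing has ended by EOT and for early stoppers it has already stopped, so the test does not shorten exposure. It cannot detect conceptions just before EOT, which is why the SFU test stays. It also cannot reach a participant who does not attend EOT.
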